### 3. STATISTICAL CONSIDERATIONS

Data will be handled and processed per the sponsor's representative (Novotech) Standard Operating Procedures (SOPs), which are written based on the principles of good clinical practice (GCP).

All data collected on the eCRFs will be presented in the data listings and will be listed and sorted by SD/MAD, treatment, subject number and visit, where applicable. All summaries will present the data by SD/MAD (apart from PK summaries), treatment group and overall (total subjects), as applicable. In addition, all placebo subjects will be combined into a single placebo group for purposes of summarizing the data.

- Continuous variables: Descriptive statistics will include the number of non-missing values (N), mean, standard deviation (SD\*), median, minimum, maximum.  
  
The minimum and maximum values will be displayed to the same decimal precision as the source data, the arithmetic mean, SD\* and median values will be displayed to one more decimal than the source data for the specific variable.  
  
The appropriate precision for derived variables will be determined based on the precision of the data on which the derivations are based, and statistics will be presented in accordance with the abovementioned rules.
- PK data: For PK data the arithmetic mean, standard deviation, median, minimum, maximum, coefficient of variation (CV%), geometric mean and geometric coefficient of variation (geo CV%) values will be presented. For the ratio of concentration data to the (within 30 minutes) pre-dose concentration on Day 1, the  $\ln(\text{SD}^*)$  will also be presented.
- Categorical variables: Descriptive statistics will include frequency counts and percentages per category. Percentages will be rounded to one decimal place, with the denominator being the number of subjects in the relevant population with non-missing data, unless otherwise specified.
- Time to Event Analysis: Through the Kaplan-Meier method, nonparametric estimates of the survivor function will be represented by quartile estimates (Q1, Median and Q3) along with 95 CIs. Product limit estimates will be presented as part of appendices to the study outputs (SAS output).
- Imputation: No missing data will be imputed.
- Baseline: Baseline values will be defined as the last valid, non-missing observation for each subject prior to the first dose of study medication. For the PK analysis, baseline will be defined as the pre-dose value for each study day.

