#### **11.8 Other safety evaluations**

Hospitalization follow-up will be presented in by-subject listings by study part and treatment group. Length of stay in hospital defined as date and time of discharge or date of study exit if still hospitalized at the time of death or study exit (censored at 23:59) - date and time of Hospitalization admission due to CAP in hours, length of ICU stay and the period of intubation in days will be listed and presented through Kaplan-Meier (K-M) methods.

The length of stay in ICU and period of intubation analysis will be restricted to subjects that stayed in the ICU and were intubated. The event investigated will be the cessation of ICU stay and the cessation of intubation.

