	SD	x.xxx	x.xxx	x.xxx	x.xxx	x.xxx	x.xxx	x.xxx	
	Minimum	x.xx	x.xx	x.xx	x.xx	x.xx	x.xx	x.xx	
	Maximum	x.xx	x.xx	x.xx	x.xx	x.xx	x.xx	x.xx	
etc.									

Note: SD: Standard Deviation

Baseline is defined as the last valid, non-missing assessment prior to first study drug administration. Unscheduled visits not included in post baseline assessments.

Programming Note:  
 Include all scheduled time points.

Clinical cut-off date: DDMMYYYY  
 Program: filepath\_name, Output: filepath\_name (version x.x) Created: DDMMYYYY HH:MM

Table 14.3.4.12.2 MAD: Summary of MMSE Score (Summary of Actual and Change from Baseline Values) by Timepoint  
Protocol: BTI-201  
Safety Population

Clinical cut-off date: DDMMYYYY  
Program: filepath\_name, Output: filepath\_name (version x.x) Created: DDMMYYYY HH:MM

Programming Note:  
Repeat Table 14.3.4.12.1  
Include all scheduled time points.  
  
Include: rhu-pGSN 6 mg/kg;  
          rhu-pGSN 12 mg/kg;  
          rhu-pGSN 24 mg/kg;  
          Combined Active;  
          Combined Placebo;  
          Overall

Table 14.3.4.13.1 SD: Summary of Hospitalization  
 Protocol: BTI-201  
 Safety Population

Parameter (Kaplan-Meier Estimates)	rhu-pGSN: 6 mg/kg (N=xx)	Placebo (N=xx)	Overall (N=xx)
Hospital Stay			
Number of Subjects Discharged	xx (xx.x%)	xx (xx.x%)	xx (xx.x%)
Number of Subjects not Discharged	xx (xx.x%)	xx (xx.x%)	xx (xx.x%)
Length of Stay in Hospital (hours) (95% CI)			
25th Percentile	xx (xx.x, xx.x)	xx (xx.x, xx.x)	xx (xx.x, xx.x)
Median	xx (xx.x, xx.x)	xx (xx.x, xx.x)	xx (xx.x, xx.x)
75th Percentile	xx (xx.x, xx.x)	xx (xx.x, xx.x)	xx (xx.x, xx.x)
ICU Stay			
Number of Subjects in ICU	xx (xx.x%)	xx (xx.x%)	xx (xx.x%)
Number of Subjects not in ICU	xx (xx.x%)	xx (xx.x%)	xx (xx.x%)
Length of Stay in ICU (days) (95% CI)			
25th Percentile	xx (xx.x, xx.x)	xx (xx.x, xx.x)	xx (xx.x, xx.x)
Median	xx (xx.x, xx.x)	xx (xx.x, xx.x)	xx (xx.x, xx.x)
75th Percentile	xx (xx.x, xx.x)	xx (xx.x, xx.x)	xx (xx.x, xx.x)
Intubation			
Number of Subjects Intubated	xx (xx.x%)	xx (xx.x%)	xx (xx.x%)
Number of Subjects not Intubated	xx (xx.x%)	xx (xx.x%)	xx (xx.x%)
Length of Intubation (days) (95% CI)			
25th Percentile	xx (xx.x, xx.x)	xx (xx.x, xx.x)	xx (xx.x, xx.x)
Median	xx (xx.x, xx.x)	xx (xx.x, xx.x)	xx (xx.x, xx.x)
75th Percentile	xx (xx.x, xx.x)	xx (xx.x, xx.x)	xx (xx.x, xx.x)

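### SAP 11.8 makes cessation the event for ICU stay and intubation but gives no rule for death; read literally, an early death counts as a short completed duration

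*SAP*

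**What the plan says.** SAP 11.8 (Other safety evaluations) covers three durations in one place. Hospital stay runs from admission to discharge, or to "date of study exit if still hospitalized at the time of death or study exit (censored at 23:59"). Discharge is therefore the event, and a subject who dies in hospital is censored.

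For the other two durations, "The event investigated will be the cessation of ICU stay and the cessation of intubation". The analysis "will be restricted to subjects that stayed in the ICU and were intubated". Section 11.8 does not mention death for these two, does not require the subject to be alive, and gives no censoring rule.

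Nothing elsewhere in the SAP fills the gap:

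- SAP Section 3 gives the general method: "nonparametric estimates of the survivor function will be represented by quartile estimates (Q1, Median and Q3) along with 95 CIs". It names no competing event.
- Mock Table 14.3.4.13.1 (repeated for MAD as 14.3.4.13.2) has the row starting "Length of Stay in ICU (days" and a matching intubation row. These are labels and define no event.
- The hospital block of that table shows those discharged and "Number of Subjects not Discharged". The other blocks show only exposure: those in the ICU against "Number of Subjects not in ICU", and "Number of Subjects Intubated" against those not intubated.
- The table footnote defines hospital stay only. The notes to Figures 14.3.3.x and 14.3.4.x restrict who is plotted and say nothing about events or censoring.

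**The concern.** Death ends an ICU stay and ends intubation. On the ordinary meaning of cessation, a subject who dies on ICU day 2 has a completed two-day stay, the same as a subject who recovers and leaves on day 2. A programmer working from this sentence has no stated basis for doing otherwise. The hospital-stay block of the same table censors that same death.

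ICU days and ventilator days are named clinical outcomes in protocol 5.2.3, and shorter durations would normally be read as better. Each cohort has 6 active and 2 placebo subjects, and only those who reach the ICU or are intubated enter these analyses. One early death can therefore set a quartile, and it moves that quartile in the direction that looks favourable. The table gives no sign that this has happened, because it does not separate deaths from live exits.

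**Working it through.** The documents state no figure for this point, so there is nothing to reproduce. The durations below are assumed and serve only to compare three ways of handling a death.

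**Three ICU subjects: exits alive on days 6 and 8, one death on day 2.** Each quartile is the first time at which the Kaplan-Meier estimate S falls to 0.75, 0.50 or 0.25.

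1. Death as the event (literal reading). S(2) = 2/3 = 0.667; S(6) = 0.667 × 1/2 = 0.333; S(8) = 0. Q1/median/Q3 = 2/6/8.
2. Death censored on day 2 (as for hospital stay). Two remain at risk on day 6. S(6) = 1/2 = 0.5; S(8) = 0. Q1 = 6 and Q3 = 8. S equals exactly 0.5 from day 6 to day 8, so the median is 6 or the midpoint 7, depending on convention. Result: 6/6-7/8.
3. Death kept at risk without the event to Day 28. S(6) = 2/3 = 0.667; S(8) = 0.667 × 1/2 = 0.333, with no further fall. Result: 6/8/not reached.

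| Handling of the death | Q1 | Median | Q3 |
|---|---|---|---|
| Event | 2 | 6 | 8 |
| Censored | 6 | 6-7 | 8 |
| Kept at risk | 6 | 8 | not reached |

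Against censoring, the literal reading is 4 days shorter at Q1, 0 to 1 day shorter at the median, and the same at Q3. Against keeping the death at risk, it is 4 days shorter at Q1 and 2 days shorter at the median.

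**Six ICU subjects: durations 2, 3, 4, 6, 8 and 10 days.** All as events, S = 0.833, 0.667, 0.5, 0.333, 0.167, 0. This gives 3/4/8 (median 5 under the midpoint convention).

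- If the day-3 exit is a death and is censored: S(2) = 5/6 = 0.833; S(4) = 0.833 × 3/4 = 0.625; S(6) = 0.625 × 2/3 = 0.417; S(8) = 0.417 × 1/2 = 0.208. Result: 4/6/8.
- If the day-10 exit is the death, S has already fallen to 0.167 by day 8, so no quartile changes.

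**Constant hazards.** Let λ be the hazard of leaving alive, μ the hazard of death, and d = μ/(λ + μ) the share of episodes that end in death. The median is ln 2/λ with death censored and ln 2/(λ + μ) with death as the event. The ratio is λ/(λ + μ) = 1 − d. For an assumed censored median of 5.0 days:

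| d | 10% | 20% | 30% | 40% | 50% |
|---|---|---|---|---|---|
| Median with death as event (days) | 4.5 | 4.0 | 3.5 | 3.0 | 2.5 |

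**The case against.** A reader might infer that the SAP states a rule for ICU stay and intubation opposite to the one for hospital stay, under which any cessation counts and death is scored as success. The documents do not support that. SAP 11.8 is silent on death for these two durations. The words any and success do not appear there, and a programmer could carry over the hospital-stay handling from the same section. What is established is a missing rule whose literal reading includes death.

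The size also depends on the comparator. The 2-day median shift arises only if deaths are kept at risk, a rule the SAP uses nowhere. Against the SAP's own hospital-stay rule the shift is 0 to 1 day. The three-subject example also makes the earliest exit the death, and the documents give no ICU or death rate to show how likely that is. Protocol 7.3 excludes intubation, vasopressor support and direct ICU admission at entry, so few such episodes may occur.

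Time actually spent in the ICU is a legitimate description of resource use, and it does end at death. The outcomes are exploratory, the outputs are quartiles with no planned between-arm test, and deaths appear in the adverse event summaries and overall survival analysis (SAP 11.1.2). Listings 16.2.7.4.x and 16.2.14.x allow a fatal ICU stay to be traced by subject.

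All of this stands and limits the impact. It does not supply the missing rule, and SAP 11.8 needs an added sentence under either reading.

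**Conclusion.** The concern holds as an incomplete event definition. SAP 11.8 does not require the subject to be alive when ICU stay or intubation ends, and it does not say how death is handled. The literal reading makes a fatal episode a completed event, whereas hospital stay is censored at death.

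The direction is clear: with death as the event, quartiles are shorter than or equal to those with death censored. The size is not fixed by the documents. In the assumed three-subject example the shift is 4 days at Q1 and 0 to 2 days at the median, depending on the comparator. Under constant hazards the median falls by the share of episodes that end in death. A late death may change nothing. The effect is confined to these rows and figures, which are exploratory and descriptive, so this is a low-cost improvement and does not threaten the trial's main conclusions.

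**What to change.** In SAP 11.8, the footnotes of Tables 14.3.4.13.x and the notes to Figures 14.3.3.x and 14.3.4.x:

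- Define the events as leaving the ICU alive and extubated alive.
- Treat death as a competing event and present the cumulative incidence of the live event, or keep subjects who die at risk without the event to Day 28. Censoring at the time of death is the weaker choice, because death is informative about whether the subject would have left alive.
- Handle death in the same way for hospital stay, so that the three durations in one table agree. Changing only ICU stay and intubation would leave the same death handled differently in adjacent blocks.
- Add rows for ICU stay and for intubation with the numbers of events, deaths and censored subjects.

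The cost is a few sentences and minor programming. Reported durations will be less favourable when deaths occur, and an upper quartile may not be reached.

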## GENERAL COMMENTS

- Unless otherwise stated, parameters will be listed in alphabetical order
- Change from Baseline:  
Change from Baseline will be calculated as:

$$\text{Change from baseline} = \text{new value} - \text{baseline value}$$

- Names and order of Treatment Groups

SD:

- Cohort 1: rhu-pGGSN 6 mg/kg;
- Cohort 1: Placebo

MAD:

- Cohort 2: rhu-pGGSN 6 mg/kg;
- Cohort 2: Placebo
- Cohort 3: rhu-pGGSN 12 mg/kg;
- Cohort 3: Placebo
- Cohort 4: rhu-pGGSN 24 mg/kg;
- Cohort 4: Placebo

- Names of visits

SD:

- Screening
- Day 1
- Day 2
- Day 3/4
- Day 7
- Day 14
- Day 28 / Early Termination (Combined visit for safety and efficacy)
- Unscheduled

MAD:

- Screening
- Day 1
- Day 2
- Day 3
- Day 4
- Day 7
- Day 14

- Day 28 / Early Termination (Combined visit for safety and efficacy)
- Unscheduled
- Column widths and text-wrapping may be altered in final output in order to best present the data
- Footnotes may be added/amended if required

Listing 16.2.1.2.1 SD: Subject Disposition  
Protocol: BTI-201  
Intent-to-Treat Population  
Cohort 1: rhu-pGSN 6 mg/kg

Subject	Final Disposition	Reason for Discontinuation	Date of Study Exit (DDMMYYYY)	Date of Last Contact (DDMMYYYY)
XXX	Withdrawn	Due to Adverse Event: AE#: XXXXXXXXXXXXXXX	DDMMYYYY	DDMMYYYY
XXX	Completed		DDMMYYYY	
XXX	Completed		DDMMYYYY	
XXX	Withdrawn	Other: XXXXXXXXXXXXXXX	DDMMYYYY	
etc.				

Clinical cut-off date: DDMMYYYY

Program: filepath\_name, Output: filepath\_name (version x.x) Created: DDMMYYYY HH:MM

Listing 16.2.1.2.2 MAD: Subject Disposition

Protocol: BTI-201

Intent-to-Treat Population

Cohort 2: rhu-pGSN 6 mg/kg

Programming Note:  
Repeat Listing 16.2.1.2.1 for MAD.

Listing 16.2.2.1 SD: Protocol Deviations  
Protocol: BTI-201  
Intent-to-Treat Population  
Cohort 1: rhu-pGSN 6 mg/kg

Subject	Type of Deviation	Date of Deviation (DDMMYYYY)	Description of Deviation
XXX	ABCD ABCD	DDMMYYYY DDMMYYYY	ABCD ABCD
..			
XXX	ABCD ABCD	DDMMYYYY DDMMYYYY	ABCD ABCD
..			
XXX	ABCD ABCD	DDMMYYYY DDMMYYYY	ABCD ABCD
..			
XXX	ABCD ABCD	DDMMYYYY DDMMYYYY	ABCD ABCD
XXX	ABCD ABCD	DDMMYYYY DDMMYYYY	ABCD ABCD

Clinical cut-off date: DDMMYYYY  
Page x of x

Program: filepath\_name, Output: filepath\_name (version x.x) Created: DDMMYYYY HH:MM

Listing 16.2.2.2 MAD: Protocol Deviations

Protocol: BTI-201

Intent-to-Treat Population

Cohort 2: rhu-pGSN 6 mg/kg

Programming Note:  
Repeat Listing 16.2.2.1 for MAD.

Listing 16.2.3.1 SD: Analysis Populations

Protocol: BTI-201

Intent-to-Treat Population

Cohort 1: rhu-pGSN 6 mg/kg

Subject	Intent-to-Treat Population	Safety Population	PK Population	Per Protocol Population
XXX	Yes	Yes	Yes	Yes
XXX	Yes	Yes	Yes	Yes
XXX	Yes	Yes	Yes	Yes
XXX	Yes	Yes	Yes	Yes
XXX	Yes	Yes	Yes	Yes
XXX	Yes	Yes	Yes	Yes
XXX	Yes	Yes	Yes	Yes
Etc.				

Clinical cut-off date: DDMMYYYY

Program: filepath\_name, Output: filepath\_name (version x.x) Created: DDMMYYYY HH:MM

Listing 16.2.3.2 MAD: Analysis Populations

Protocol: BTI-201

Intent-to-Treat Population

Cohort 2: rhu-pGSN 6 mg/kg

Programming Note:  
Repeat Listing 16.2.3.1 for MAD.

Listing 16.2.4.1.1 SD: Demographics and Baseline Characteristics  
 Protocol: BTI-201  
 Intent-to-Treat Population

Cohort 1: rhu-pGSN 6 mg/kg

Subject	Date of Informed Consent (DDMMYYYY)	Protocol Version	Date of Birth (DDMMYYYY)	Age at Informed Consent	Sex	Child Bearing Potential	Contraceptive Methods	Race	Height (cm)	Weight (kg)
XXX	DDMMYYYY	Amendment 1	DDMMYYYY	xx	Male			White	xxx	xx.x
XXX	DDMMYYYY	Amendment 1	DDMMYYYY	xx	Female	No		White	xxx	xx.x
XXX	DDMMYYYY	Amendment 1	DDMMYYYY	xx	Male		Hormonal	White	xxx	xx.x
XXX	DDMMYYYY	Amendment 1	DDMMYYYY	xx	Female	Yes	methods	Other: XXXXXXXXXX	xxx	xx.x
etc.										

Clinical cut-off date: DDMMYYYY

Program: filepath\_name, Output: filepath\_name (version x.x) Created: DDMMYYYY HH:MM

Listing 16.2.4.1.1.2 MAD: Demographics and Baseline Characteristics

Protocol: BTI-201

Intent-to-Treat Population

Cohort 2: rhu-pGSN 6 mg/kg

Programming Note:  
Repeat Listing 16.2.4.1.1 for MAD.

Listing 16.2.4.2.1 SD: Viral Serology  
 Protocol: BTI-201  
 Intent-to-Treat Population

Cohort 1: rhu-pGSN 6 mg/kg

Subject	Visit	Visit Date (DDMMYYYY)	Test	Result	Most Recent Viral Load (unit)	Most Recent CD4 Count (unit)
XXX	Screening	DDMMYYYY	HIV Hepatitis B Surface Antigen Hepatitis C	Negative Negative Negative	xxxxxx	xxx.x
XXX	Screening	DDMMYYYY	HIV Hepatitis B Surface Antigen Hepatitis C	Negative Negative Negative	xxxxxx	xxx.x
etc.						

Clinical cut-off date: DDMMYYYY

Program: filepath\_name, Output: filepath\_name (version x.x) Created: DDMMYYYY HH:MM

Listing 16.2.4.2.2 MAD: Viral Serology

Protocol: BTI-201

Intent-to-Treat Population

Cohort 2: rhu-pGSN 6 mg/kg

Programming Note:  
Repeat Listing 16.2.4.2.1 for MAD.

Listing 16.2.4.3.1 SD: Medical History  
 Protocol: BTI-201  
 Intent-to-Treat Population  
 Cohort 1: rhu-pGSN 6 mg/kg

Subject	Condition/ Body System	System Organ Class / Preferred Term	Date of Diagnosis (DDMMYYYY)	Resolution Date (DDMMYYYY)	Concomitant Medication Taken	Ongoing
XXX	XXXXXXXXXXXX/ YYYYYYYYYYY	XXXXXXXXXX/ YYYYYYYY/ ZZZZZZZZ	DDMMYYYY	DDMMYYYY	No	No
XXX	XXXXXXXXXXXX/ YYYYYYYYYYY	XXXXXXXXXX/ YYYYYYYY/ ZZZZZZZZ	DDMMYYYY	DDMMYYYY	Yes	Yes
...						
XXX	XXXXXXXXXXXX/ YYYYYYYYYYY	XXXXXXXXXX/ YYYYYYYY/ ZZZZZZZZ	DDMMYYYY	DDMMYYYY	No	No
XXX	XXXXXXXXXXXX/ YYYYYYYYYYY	XXXXXXXXXX/ YYYYYYYY/ ZZZZZZZZ	DDMMYYYY	DDMMYYYY	No	No
...						
XXX	XXXXXXXXXXXX/ YYYYYYYYYYY	XXXXXXXXXX/ YYYYYYYY/ ZZZZZZZZ	DDMMYYYY	DDMMYYYY	No	No
XXX	XXXXXXXXXXXX/ YYYYYYYYYYY	XXXXXXXXXX/ YYYYYYYY/ ZZZZZZZZ	DDMMYYYY	DDMMYYYY	No	No

Note: MedDRA Version XX.X

Clinical cut-off date: DDMMYYYY

Program: filepath\_name, Output: filepath\_name (version x.x) Created: DDMMYYYY HH:MM

Listing 16.2.4.3.2 MAD: Medical History

Protocol: BTI-201

Intent-to-Treat Population

Cohort 2: rhu-pGSN 6 mg/kg

Programming Note:  
Repeat Listing 16.2.4.3.1 for MAD.

Listing 16.2.4.4.1 SD: Pregnancy Test Results  
 Protocol: BTI-201  
 Intent-to-Treat Population  
 Cohort 1: rhu-pGSN 6 mg/kg

Subject	Assessment Performed - Reason Not Performed	Visit	Sample Date/ Time (DDMMYY/ HH:MM)	Sample Type	Result
XXX	Yes	Screening	DDMMYY/ HH:MM	Serum	Negative
		Day 1	DDMMYY/ HH:MM	Urine	Negative
		Day 28 / Early Termination	DDMMYY/ HH:MM	Urine	Negative
XXX	Yes	Screening	DDMMYY/ HH:MM	Serum	Negative
		Day 1	DDMMYY/ HH:MM	Urine	Negative
		Day 28 / Early Termination	DDMMYY/ HH:MM	Urine	Negative
XXX	Yes	Screening	DDMMYY/ HH:MM	Serum	Negative
		Day 1	DDMMYY/ HH:MM	Urine	Negative
		Day 28 / Early Termination	DDMMYY/ HH:MM	Urine	Negative

etc.

Clinical cut-off date: DDMMYYYY

Program: filepath\_name, Output: filepath\_name (version x.x) Created: DDMMYYYY HH:MM

Listing 16.2.4.4.2 MAD: Pregnancy Test Results

Protocol: BTI-201

Intent-to-Treat Population

Cohort 2: rhu-pGSN 6 mg/kg

Programming Note:  
Repeat Listing 16.2.4.4.1 for MAD.

Listing 16.2.4.5.1 SD: Confirmation of CAP

Protocol: BTI-201

Intent-to-Treat Population

Cohort 1: rhu-pGSN 6 mg/kg

Subject	Visit	Visit Date (DDMMYY)	Was there clinical confirmation of CAP	Was there radiological confirmation of CAP (CXR or CT)	Was CXR or CT Scan Performed: Date (DDMMYY)	CXR or CT Scan Findings	Date and Time of presentation to the hospital (DDMMYY/HH:MM)	Date and Time of Hospitalization Admission due to CAP (DDMMYY/HH:MM)	Subject Randomized
XXX	Screening	DDMMYYYY	Yes	Yes	Yes: DDMMYYYY	XXXXXXXXXX	DDMMYYYY/HH:MM	DDMMYYYY/HH:MM	Yes
XXX	Screening	DDMMYYYY	Yes	Yes	Yes: DDMMYYYY	XXXXXXXXXX	DDMMYYYY/HH:MM	DDMMYYYY/HH:MM	Yes
XXX	Screening	DDMMYYYY	Yes	Yes	Yes: DDMMYYYY	XXXXXXXXXX	DDMMYYYY/HH:MM	DDMMYYYY/HH:MM	Yes
etc.									

Clinical cut-off date: DDMMYYYY

Program: filepath\_name, Output: filepath\_name (version x.x) Created: DDMMYYYY HH:MM

Listing 16.2.4.5.2 MAD: Confirmation of CAP

Protocol: BTI-201

Intent-to-Treat Population

Cohort 2: rhu-pGSN 6 mg/kg

Programming Note:  
Repeat Listing 16.2.4.5.2 for MAD.

Listing 16.2.4.6.1 SD: Eligibility Assessment  
Protocol: BTI-201  
Intent-to-Treat Population

Cohort 1: rhu-pGSN 6 mg/kg

Subject	Eligibility Assessment Date (DDMMYYYY)	Did the patient meet all		Inclusion criterion not met	Did the patient meet all		Exclusion Criterion not met
		inclusion criteria?	exclusion criteria?		exclusion criteria?	exclusion criteria?	
XXX	DDMMYYYY	Yes				Yes	
XXX	DDMMYYYY	Yes				Yes	
XXX	DDMMYYYY	Yes				Yes	
XXX	DDMMYYYY	Yes				Yes	
XXX	DDMMYYYY	Yes				Yes	
XXX	DDMMYYYY	Yes				Yes	

Clinical cut-off date: DDMMYYYY

Program: filepath\_name, Output: filepath\_name (version x.x) Created: DDMMYYYY HH:MM

Listing 16.2.4.6.2 MAD: Eligibility Criteria

Protocol: BTI-201

Intent-to-Treat Population

Cohort 2: rhu-pGSN 6 mg/kg

Programming Note:  
Repeat Listing 16.2.4.6.1 for MAD.

Listing 16.2.4.7.1 SD: Prior Medications  
 Protocol: BTI-201  
 Intent-to-Treat Population

Cohort 1: rhu-pGSN 6 mg/kg

Subject Number	CM#	Drug Name/ATC3/PT	Indication	Start Date/ Stop Date (DDMMYYYY)	Ongoing	Dose	Unit	Frequency	Route
XXX	1	XXXXXXXXXXXXXXXXXXXX/ ZZZZZZZZZZZZZZZZZZZZ/ YYYYYYYYYYYYYYYYYYYY	Pre-existing condition: MH#	DDMMYYYY / DDMMYYYY	No	XX	Unit	YYYYYY	ZZZZZ
	2	XXXXXXXXXXXXXXXXXXXX/ ZZZZZZZZZZZZZZZZZZZZ/ YYYYYYYYYYYYYYYYYYYY	Other: YYYYYY	DDMMYYYY / DDMMYYYY	No	XX	Unit	YYYYYY	ZZZZZ
XXX	1	XXXXXXXXXXXXXXXXXXXX/ ZZZZZZZZZZZZZZZZZZZZ/ YYYYYYYYYYYYYYYYYYYY	Other: YYYYYY	DDMMYYYY / DDMMYYYY	No	XX	Unit	YYYYYY	ZZZZZ
	2	XXXXXXXXXXXXXXXXXXXX/ ZZZZZZZZZZZZZZZZZZZZ/ YYYYYYYYYYYYYYYYYYYY	Other: YYYYYY	DDMMYYYY / DDMMYYYY	No	XX	Unit	YYYYYY	ZZZZZ
XXX	1	XXXXXXXXXXXXXXXXXXXX/ ZZZZZZZZZZZZZZZZZZZZ/ YYYYYYYYYYYYYYYYYYYY	Pre-existing condition: MH#	DDMMYYYY / DDMMYYYY	No	XX	Unit	YYYYYY	ZZZZZ

Etc.

Note: Prior medications are defined as any medication where the use was stopped prior to the first administration of the study medication.  
 WHO-DD, xxxxxxxxxx

Clinical cut-off date: DDMMYYYY

Program: filepath\_name, Output: filepath\_name (version x.x) Created: DDMMYYYY HH:MM

Listing 16.2.4.7.2 MAD: Prior Medications

Protocol: BTI-201

Intent-to-Treat Population

Cohort 2: rhu-pGSN 6 mg/kg

Programming Note:  
Repeat Listing 16.2.4.7.1 for MAD.

Listing 16.2.5.1.1 SD: Randomization  
Protocol: BTI-201  
Intent-to-Treat Population  
Cohort 1: rhu-pGSN 6 mg/kg

Subject	Date /Time of Randomization (DDMMYYYY/ HH:MM)	Randomization Number	Date /Time of Emergency Unblinding (DDMMYYYY/ HH:MM)	Reason for Emergency Unblinding
XXX	DDMMYYYY/ HH:MM	XXXXX		
XXX	DDMMYYYY/ HH:MM	XXXXX		
XXX	DDMMYYYY/ HH:MM	XXXXX		
XXX	DDMMYYYY/ HH:MM	XXXXX	DDMMYYYY/ HH:MM	XXXXXXXXXXXXXXXXXXXXXXXXXXXX
XXX	DDMMYYYY/ HH:MM	XXXXX		
XXX	DDMMYYYY/ HH:MM	XXXXX		
etc.				

Clinical cut-off date: DDMMYYYY

Program: filepath\_name, Output: filepath\_name (version x.x) Created: DDMMYYYY HH:MM

Listing 16.2.5.1.1.2 MAD: Randomization

Protocol: BTI-201

Intent-to-Treat Population

Cohort 2: rhu-pGSN 6 mg/kg

Programming Note:  
Repeat Listing 16.2.5.1.1 for MAD.

Listing 16.2.5.2.1 SD: Study Drug Administration  
 Protocol: BTI-201  
 Intent-to-Treat Population

Cohort 1: rhu-pGSN 6 mg/kg

Subject	Visit	Was Study Drug Administered? (If no, provide reason)	Start Date/ Time of Injection (DDMMYYYY/ HH:MM)	Stop Date/ Time of Injection (DDMMYYYY/ HH:MM)	Study Drug Administered per Dose Prescribed	Reason not Successfully Administered	Volume Administered (mL)	Total Duration of Injection (Including Interruptions - minutes)
XXX	Day 1	Yes	DDMMYYYY/ HH:MM	DDMMYYYY/ HH:MM	Yes		xx	xx
XXX	Day 1	Yes	DDMMYYYY/ HH:MM	DDMMYYYY/ HH:MM	Yes		xx	xx
XXX	Day 1	Yes	DDMMYYYY/ HH:MM	DDMMYYYY/ HH:MM	No	XXXXXXXXXXXXXX	xx	
XXX	Day 1	Yes	DDMMYYYY/ HH:MM	DDMMYYYY/ HH:MM	Yes		xx	xx
XXX	Day 1	Yes	DDMMYYYY/ HH:MM	DDMMYYYY/ HH:MM	Yes		xx	xx
XXX	Day 1	No - XXXXXXXXXX						

Clinical cut-off date: DDMMYYYY

Program: filepath\_name, Output: filepath\_name (version x.x) Created: DDMMYYYY HH:MM

Listing 16.2.5.2.2 MAD: Study Drug Administration  
 Protocol: BTI-201  
 Intent-to-Treat Population

Cohort 2: rhu-pGSN 6 mg/kg

Subject	Visit	Was Study Drug Administered? (If no, provide reason)	Start Date/ Time of Injection (DDMMYYYY/ HH:MM)	Stop Date/ Time of Injection (DDMMYYYY/ HH:MM)	Study Drug Administered per Dose Prescribed	Reason not Successfully Administered	Volume Administered (mL)	Total Duration of Injection (Including Interruptions - minutes)
XXX	Day 1	Yes	DDMMYYYY/ HH:MM	DDMMYYYY/ HH:MM	Yes		xx	xx
	Day 2	Yes	DDMMYYYY/ HH:MM	DDMMYYYY/ HH:MM	Yes		xx	xx
	Day 3	Yes	DDMMYYYY/ HH:MM	DDMMYYYY/ HH:MM	No	XXXXXXXXXXXXXX	xx	xx
XXX	Day 1	Yes	DDMMYYYY/ HH:MM	DDMMYYYY/ HH:MM	Yes		xx	xx
	Day 2	Yes	DDMMYYYY/ HH:MM	DDMMYYYY/ HH:MM	Yes		xx	xx
	Day 3	No - XXXXXXXXXX						

Clinical cut-off date: DDMMYYYY

Program: filepath\_name, Output: filepath\_name (version x.x) Created: DDMMYYYY HH:MM

Listing 16.2.5.3.1 SD: Study Drug Interruption  
Protocol: BTI-201  
Intent-to-Treat Population

Cohort 1: rhu-pGSN 6 mg/kg

Subject	Visit	Interruption	Date and Time of Interruption (DDMMYYYY/ HH:MM)	Date and Time of Injection Re-start (DDMMYYYY/ HH:MM)	Reason for Interruption
XXX	Day 1	1	DDMMYYYY/ HH:MM	DDMMYYYY/ HH:MM	XX
XXX	Day 1	1	DDMMYYYY/ HH:MM	DDMMYYYY/ HH:MM	XX
		2			
XXX	Day 1	1	DDMMYYYY/ HH:MM	DDMMYYYY/ HH:MM	XX
XXX	Day 1	1	DDMMYYYY/ HH:MM	DDMMYYYY/ HH:MM	XX
XXX	Day 1	1	DDMMYYYY/ HH:MM	DDMMYYYY/ HH:MM	XX

Clinical cut-off date: DDMMYYYY

Program: filepath\_name, Output: filepath\_name (version x.x) Created: DDMMYYYY HH:MM

Listing 16.2.5.3.2 MAD: Study Drug Interruption

Protocol: BTI-201

Intent-to-Treat Population

Cohort 1: rhu-pGSN 6 mg/kg

Subject	Visit	Interruption	Date and Time of Interruption (DDMMYYYY/ HH:MM)	Date and Time of Injection Re-start (DDMMYYYY/ HH:MM)	Reason for Interruption
XXX	Day 1	1	DDMMYYYY/ HH:MM	DDMMYYYY/ HH:MM	XX
XXX	Day 2	1	DDMMYYYY/ HH:MM	DDMMYYYY/ HH:MM	XX
XXX	Day 1	1	DDMMYYYY/ HH:MM	DDMMYYYY/ HH:MM	XX
XXX	Day 3	1	DDMMYYYY/ HH:MM	DDMMYYYY/ HH:MM	XX
XXX	Day 1	1	DDMMYYYY/ HH:MM	DDMMYYYY/ HH:MM	XX

Clinical cut-off date: DDMMYYYY

Program: filepath\_name, Output: filepath\_name (version x.x) Created: DDMMYYYY HH:MM

Listing 16.2.6.1.1 SD: Individual pGSN Plasma Concentrations (unit)

Protocol: BTI-201

Intent-to-Treat Population

Cohort 1: rhu-pGSN 6 mg/kg

Subject Number	Day	Date/Time of Dose on Dosing Day (DDMMYYYY/HH:MM)	Sampling Time	Was PK Sample Collected?	Date of PK Sample Collection (DDMMYYYY)	Time of PK Sample Collection (HH:MM)	Time Deviation	Concentration (ng/mL)	Ratio from Pre-Injection Day 1	Ratio from Pre-Injection	Comments
XXX	1	DDMMYYYY/HH:MM	Pre-Injection	Yes	DDMMYYYY	HH:MM	xx mins	XXX	X.XX	X.XX	YYYYYYYY
			5 to 10 mins post	Yes	DDMMYYYY	HH:MM	xx mins	XXX	X.XX	X.XX	
			2 hours post	Yes	DDMMYYYY	HH:MM	xx hours	XXX	X.XX	X.XX	
			8 hours post	Yes	DDMMYYYY	HH:MM	xx hours	XXX	X.XX	X.XX	
			12 hours post	Yes	DDMMYYYY	HH:MM	xx hours	XXX	X.XX	X.XX	
			16 hours post	Yes	DDMMYYYY	HH:MM	xx hours	XXX	X.XX	X.XX	
			24 hours post	Yes	DDMMYYYY	HH:MM	xx hours	XXX	X.XX	X.XX	
XXX	1	DDMMYYYY/HH:MM	Pre-Injection	Yes	DDMMYYYY	HH:MM	xx mins	XXX	X.XX	X.XX	YYYYYYYY
			5 to 10 mins post	Yes	DDMMYYYY	HH:MM	xx mins	XXX	X.XX	X.XX	
			2 hours post	Yes	DDMMYYYY	HH:MM	xx hours	XXX	X.XX	X.XX	
			8 hours post	Yes	DDMMYYYY	HH:MM	xx hours	XXX	X.XX	X.XX	
			12 hours post	Yes	DDMMYYYY	HH:MM	xx hours	XXX	X.XX	X.XX	
			16 hours post	Yes	DDMMYYYY	HH:MM	xx hours	XXX	X.XX	X.XX	
			24 hours post	Yes	DDMMYYYY	HH:MM	xx hours	XXX	X.XX	X.XX	

Clinical cut-off date: DDMMYYYY

Program: filepath\_name, Output: filepath\_name (version x.x) Created: DDMMYYYY HH:MM

Listing 16.2.6.1.1.2 MAD: Individual pGSN Plasma Concentrations (unit)  
 Protocol: BTI-201  
 Intent-to-Treat Population

Cohort 1: rhu-pGSN 6 mg/kg

Subject Number	Day	Date/Time of Dose on Dosing Day (DDMMYYYY/HH:MM)	Sampling Time	Was PK Sample Collected?	Date of PK Sample Collection (DDMMYYYY)	Time of PK Sample Collection (HH:MM)	Time Deviation	Concentration (ng/mL)	Ratio from Pre-Injection Day 1	Ratio from Pre-Injection	Comments
XXX	1	DDMMYYYY/HH:MM	Pre-Injection	Yes	DDMMYYYY	HH:MM	xx mins	XXX	X.XX	X.XX	YYYYYYYY
			5 to 10 mins post	Yes	DDMMYYYY	HH:MM	xx mins	XXX	X.XX	X.XX	
			2 hours post	Yes	DDMMYYYY	HH:MM	xx hours	XXX	X.XX	X.XX	
			8 hours post	Yes	DDMMYYYY	HH:MM	xx hours	XXX	X.XX	X.XX	
			12 hours post	Yes	DDMMYYYY	HH:MM	xx hours	XXX	X.XX	X.XX	
			16 hours post	Yes	DDMMYYYY	HH:MM	xx hours	XXX	X.XX	X.XX	
			24 hours post	Yes	DDMMYYYY	HH:MM	xx hours	XXX	X.XX	X.XX	
	2	DDMMYYYY/HH:MM	Pre-Injection	Yes	DDMMYYYY	HH:MM	xx mins	XXX	X.XX	X.XX	YYYYYYYY
			5 to 10 mins post	Yes	DDMMYYYY	HH:MM	xx mins	XXX	X.XX	X.XX	
			2 hours post	Yes	DDMMYYYY	HH:MM	xx hours	XXX	X.XX	X.XX	
			8 hours post	Yes	DDMMYYYY	HH:MM	xx hours	XXX	X.XX	X.XX	
			12 hours post	Yes	DDMMYYYY	HH:MM	xx hours	XXX	X.XX	X.XX	
			16 hours post	Yes	DDMMYYYY	HH:MM	xx hours	XXX	X.XX	X.XX	
			24 hours post	Yes	DDMMYYYY	HH:MM	xx hours	XXX	X.XX	X.XX	

Clinical cut-off date: DDMMYYYY

Program: filepath\_name, Output: filepath\_name (version x.x) Created: DDMMYYYY HH:MM

Listing 16.2.6.2.1 SD: Individual Estimated Plasma rhu-pGSN Concentrations (unit)  
 Protocol: BTI-201  
 Intent-to-Treat Population

Cohort 1: rhu-pGSN 6 mg/kg

Subject Number	Day	Date/Time of Dose on Dosing Day (DDMMYYYY/HH:MM)	Sampling Time	Was PK Sample Collected?	Date of PK Sample Collection (DDMMYYYY)	Time of PK Sample Collection (HH:MM)	Time Deviation	Concentration (ng/mL)	Change from Pre-Injection Day 1	Change from Pre-Injection) - (Mean Placebo Change from Pre-Injection)	Comments
XXX	1	DDMMYYYY/HH:MM	Pre-Injection	Yes	DDMMYYYY	HH:MM	xx mins	XXX	XXX	YYYYYY	
			5 to 10 mins post	Yes	DDMMYYYY	HH:MM	xx mins	XXX	X.XX	X.XX	
			2 hours post	Yes	DDMMYYYY	HH:MM	xx hours	XXX	X.XX	X.XX	
			8 hours post	Yes	DDMMYYYY	HH:MM	xx hours	XXX	X.XX	X.XX	
			12 hours post	Yes	DDMMYYYY	HH:MM	xx hours	XXX	X.XX	X.XX	
			16 hours post	Yes	DDMMYYYY	HH:MM	xx hours	XXX	X.XX	X.XX	
			24 hours post	Yes	DDMMYYYY	HH:MM	xx hours	XXX	X.XX	X.XX	
XXX	1	DDMMYYYY/HH:MM	Pre-Injection	Yes	DDMMYYYY	HH:MM	xx mins	XXX	XXX	YYYYYY	
			5 to 10 mins post	Yes	DDMMYYYY	HH:MM	xx mins	XXX	X.XX	X.XX	
			2 hours post	Yes	DDMMYYYY	HH:MM	xx hours	XXX	X.XX	X.XX	
			8 hours post	Yes	DDMMYYYY	HH:MM	xx hours	XXX	X.XX	X.XX	
			12 hours post	Yes	DDMMYYYY	HH:MM	xx hours	XXX	X.XX	X.XX	
			16 hours post	Yes	DDMMYYYY	HH:MM	xx hours	XXX	X.XX	X.XX	
			24 hours post	Yes	DDMMYYYY	HH:MM	xx hours	XXX	X.XX	X.XX	

Clinical cut-off date: DDMMYYYY

Program: filepath\_name, Output: filepath\_name (version x.x) Created: DDMMYYYY HH:MM

Listing 16.2.6.2.2 MAD: Individual Estimated Plasma rhu-pGSN Concentrations (unit)  
 Protocol: BTI-201  
 Intent-to-Treat Population

Cohort 1: rhu-pGSN 6 mg/kg

Subject Number	Day	Date/Time of Dose on Dosing Day (DDMMYYYY/HH:MM)	Sampling Time	Was PK Sample Collected?	Date of PK Sample Collection (DDMMYYYY)	Time of PK Sample Collection (HH:MM)	Time Deviation	Concentration (ng/mL)	Change from Pre-Injection Day 1	(Change from Pre-Injection) - (Mean Placebo Change from Pre-Injection)	Comments
XXX	1	DDMMYYYY/HH:MM	Pre-Injection	Yes	DDMMYYYY	HH:MM	xx mins	XXX			YYYYYYYY
			5 to 10 mins post	Yes	DDMMYYYY	HH:MM	xx mins	XXX	X.XX	X.XX	
			2 hours post	Yes	DDMMYYYY	HH:MM	xx hours	XXX	X.XX	X.XX	
			8 hours post	Yes	DDMMYYYY	HH:MM	xx hours	XXX	X.XX	X.XX	
			12 hours post	Yes	DDMMYYYY	HH:MM	xx hours	XXX	X.XX	X.XX	
			16 hours post	Yes	DDMMYYYY	HH:MM	xx hours	XXX	X.XX	X.XX	
			24 hours post	Yes	DDMMYYYY	HH:MM	xx hours	XXX	X.XX	X.XX	
	2	DDMMYYYY/HH:MM	Pre-Injection	Yes	DDMMYYYY	HH:MM	xx mins	XXX			
			5 to 10 mins post	Yes	DDMMYYYY	HH:MM	xx mins	XXX	X.XX	X.XX	YYYYYYYY
			2 hours post	Yes	DDMMYYYY	HH:MM	xx hours	XXX	X.XX	X.XX	
			8 hours post	Yes	DDMMYYYY	HH:MM	xx hours	XXX	X.XX	X.XX	
			12 hours post	Yes	DDMMYYYY	HH:MM	xx hours	XXX	X.XX	X.XX	
			16 hours post	Yes	DDMMYYYY	HH:MM	xx hours	XXX	X.XX	X.XX	
			24 hours post	Yes	DDMMYYYY	HH:MM	xx hours	XXX	X.XX	X.XX	

Clinical cut-off date: DDMMYYYY

Program: filepath\_name, Output: filepath\_name (version x.x) Created: DDMMYYYY HH:MM

Listing 16.2.6.3.1 SD: Individual pGSN Plasma PK Parameters  
 Protocol: BTI-201  
 Intent-to-Treat Population

Cohort 1: rhu-pGSN 6 mg/kg

Day 1

Subject Number	AUC 0-t (unit)	AUC 0-8h (unit)	AUC 0-inf (unit)	C max (unit)	T max (unit)	k el (unit)	t 1/2 (unit)	CL/F (unit)	V z /F (unit)	%AUC ext	DN_AUC 0-t	DN_AUC 0-8	DN_AUC 0-inf	DN_C max
XXX	xx.x	xx.x	xx.x	xx.x	xx.x	xx.x	xx.x	xx.x	xx.x	xx.x	xx.x	xx.x	xx.x	xx.x
XXX	xx.x	xx.x	xx.x	xx.x	xx.x	xx.x	xx.x	xx.x	xx.x	xx.x	xx.x	xx.x	xx.x	xx.x
XXX	xx.x	xx.x	xx.x	xx.x	xx.x	xx.x	xx.x	xx.x	xx.x	xx.x	xx.x	xx.x	xx.x	xx.x
XXX	xx.x	xx.x	xx.x	xx.x	xx.x	xx.x	xx.x	xx.x	xx.x	xx.x	xx.x	xx.x	xx.x	xx.x
XXX	xx.x	xx.x	xx.x	xx.x	xx.x	xx.x	xx.x	xx.x	xx.x	xx.x	xx.x	xx.x	xx.x	xx.x
XXX	xx.x	xx.x	xx.x	xx.x	xx.x	xx.x	xx.x	xx.x	xx.x	xx.x	xx.x	xx.x	xx.x	xx.x

...

Clinical cut-off date: DDMMYYYY

Program: filepath\_name, Output: filepath\_name (version x.x) Created: DDMMYYYY HH:MM

Listing 16.2.6.3.2 MAD: Individual pGSN Plasma PK Parameters by Day  
 Protocol: BTI-201  
 Intent-to-Treat Population

Cohort 1: rhu-pGSN 6 mg/kg

Day 1

Subject Number	AUC 0-t (unit)	AUC 0-8h (unit)	AUC 0-inf (unit)	C max (unit)	T max (unit)	k el (unit)	t 1/2 (unit)	CL/F (unit)	V z /F (unit)	%AUC ext	DN_AUC 0-t	DN_AUC 0-8	DN_AUC 0-inf	DN_C max
XXX	xx.x	xx.x	xx.x	xx.x	xx.x	xx.x	xx.x	xx.x	xx.x	xx.x	xx.x	xx.x	xx.x	xx.x
XXX	xx.x	xx.x	xx.x	xx.x	xx.x	xx.x	xx.x	xx.x	xx.x	xx.x	xx.x	xx.x	xx.x	xx.x
XXX	xx.x	xx.x	xx.x	xx.x	xx.x	xx.x	xx.x	xx.x	xx.x	xx.x	xx.x	xx.x	xx.x	xx.x
XXX	xx.x	xx.x	xx.x	xx.x	xx.x	xx.x	xx.x	xx.x	xx.x	xx.x	xx.x	xx.x	xx.x	xx.x
XXX	xx.x	xx.x	xx.x	xx.x	xx.x	xx.x	xx.x	xx.x	xx.x	xx.x	xx.x	xx.x	xx.x	xx.x
XXX	xx.x	xx.x	xx.x	xx.x	xx.x	xx.x	xx.x	xx.x	xx.x	xx.x	xx.x	xx.x	xx.x	xx.x

...

Clinical cut-off date: DDMMYYYY

Program: filepath\_name, Output: filepath\_name (version x.x) Created: DDMMYYYY HH:MM

Listing 16.2.6.4.1 SD: Individual Estimated Plasma rhu-pGSN PK Parameters  
 Protocol: BTI-201  
 Intent-to-Treat Population

Cohort 1: rhu-pGSN 6 mg/kg

Day 1

Change from Pre-Injection

Double Delta Analysis

Subject Number	AUC 0-t (unit)	AUC 0-8h (unit)	C max (unit)	DN_AUC 0-t	DN_AUC 0-8	DN_C max	AUC 0-t (unit)	AUC 0-8h (unit)	C max (unit)	DN_AUC 0-t	DN_AUC 0-8	DN_C max
XXX	xx.x	xx.x	xx.x	xx.x	xx.x	xx.x	xx.x	xx.x	xx.x	xx.x	xx.x	xx.x
XXX	xx.x	xx.x	xx.x	xx.x	xx.x	xx.x	xx.x	xx.x	xx.x	xx.x	xx.x	xx.x
XXX	xx.x	xx.x	xx.x	xx.x	xx.x	xx.x	xx.x	xx.x	xx.x	xx.x	xx.x	xx.x
XXX	xx.x	xx.x	xx.x	xx.x	xx.x	xx.x	xx.x	xx.x	xx.x	xx.x	xx.x	xx.x
XXX	xx.x	xx.x	xx.x	xx.x	xx.x	xx.x	xx.x	xx.x	xx.x	xx.x	xx.x	xx.x
XXX	xx.x	xx.x	xx.x	xx.x	xx.x	xx.x	xx.x	xx.x	xx.x	xx.x	xx.x	xx.x

...

Clinical cut-off date: DDMMYYYY

Program: filepath\_name, Output: filepath\_name (version x.x) Created: DDMMYYYY HH:MM

Listing 16.2.6.4.2 MAD: Individual Estimated Plasma rhu-pGSN PK Parameters by Day  
 Protocol: BTI-201  
 Intent-to-Treat Population

Cohort 1: rhu-pGSN 6 mg/kg

Day 1

Change from Pre-Injection

Double Delta Analysis

Subject Number	AUC 0-t (unit)	AUC 0-8h (unit)	C max (unit)	DN_AUC 0-t	DN_AUC 0-8	DN_C max	AUC 0-t (unit)	AUC 0-8h (unit)	C max (unit)	DN_AUC 0-t	DN_AUC 0-8	DN_C max
XXX	xx.x	xx.x	xx.x	xx.x	xx.x	xx.x	xx.x	xx.x	xx.x	xx.x	xx.x	xx.x
XXX	xx.x	xx.x	xx.x	xx.x	xx.x	xx.x	xx.x	xx.x	xx.x	xx.x	xx.x	xx.x
XXX	xx.x	xx.x	xx.x	xx.x	xx.x	xx.x	xx.x	xx.x	xx.x	xx.x	xx.x	xx.x
XXX	xx.x	xx.x	xx.x	xx.x	xx.x	xx.x	xx.x	xx.x	xx.x	xx.x	xx.x	xx.x
XXX	xx.x	xx.x	xx.x	xx.x	xx.x	xx.x	xx.x	xx.x	xx.x	xx.x	xx.x	xx.x
XXX	xx.x	xx.x	xx.x	xx.x	xx.x	xx.x	xx.x	xx.x	xx.x	xx.x	xx.x	xx.x

...

Clinical cut-off date: DDMMYYYY

Program: filepath\_name, Output: filepath\_name (version x.x) Created: DDMMYYYY HH:MM

Listing 16.2.6.5.1 SD: Anti-rhu-pGSN Antibodies

Protocol: BTI-201

Intent-to-Treat Population

Cohort 1: rhu-pGSN 6 mg/kg

